Acute diarrhoeal diseases are a major health problem in developing countries. Infection with enterotoxigenic *Escherichia coli* (ETEC) is one of the most common causes of diarrhoea among children in developing countries and it also contributes to malnutrition. The prevalence of toxin types and colonization factors (CFs) was recently studied in fresh samples (n=4662) obtained from a 2% routine surveillance of diarrheal stools for two years from September 1996 to August 1998. It was observed that the prevalence of ETEC was 14% with over 70% isolated in children 0-5 years age range, of whom 93% were in the 0-3 years age range. The study showed that the isolation of ETEC increased in the children from as early as 3 months of age. Thus of all incidences more than 65% can be expected to occur in children < 3 years of age.

The infection could by prevented by a safe and immunogenic vaccine that is protective in children. One such vaccine undergoing evaluation is the oral inactivated ETEC vaccine consisting of recombinant cholera toxin B subunit (BS) and a mixture of formalin- inactivated whole cell ETEC bacteria expressing colonization factors (BS-CFA ETEC vaccine). The vaccine has been tested in a number of countries in phase-I safety and immunogenicity trails in adults ([name] et al., 1997). These initial vaccine trials have been extended in Egypt to larger field based phase II and phase III studies. In addition Phase III trials of vaccine efficacy are ongoing which include United States travellers to Latin America (WHO, 1999). The vaccine is being extensively studied in Egypt where it has been tested in adults as well as in children in the 2-12 years old age group (Savarino et al. 1998, 1999) and is now being tested in 6-18 months old children (WHO, 1999). A phase I study carried out in Bangladeshi children in the 3-10 year range has shown that the vaccine is safe and immunogenic (Qadri et al., manuscript submitted). Thus a phase-II safety and immunogenicity study now needs to be carried out in Bangladesh in children from 6 months to 3 years of age. Based on the results of this study the vaccine can subsequently be extended to smaller children (i.e. from 3 months of age to 3 years) in a larger phase III, protective efficacy trial.

| Princi | pal Investigato | r: Last, | first, middle |      |      |  |
|--------|-----------------|----------|---------------|------|------|--|
| PHIIC  | hai mvesnkaro   | 1. LäSt, | mst, muute    | 
 | 
 |  |

## DESCRIPTION OF THE RESEARCH PROJECT

# Hypothesis to be tested:

Concisely list in order, in the space provided, the hypothesis to be tested and the Specific Aims of the proposed study. Provide the scientific basis of the hypothesis, critically examining the observations leading to the formulation of the hypothesis.

One of the strategies for the prevention of ETEC diarrhoea is the design of a suitable and protective vaccine. Children who suffer most from the consequences of the repeated episodes of the disease will benefit most from such a vaccine. A candidate vaccine undergoing evaluation is the oral inactivated ETEC vaccine consisting of recombinant cholera toxin B sub-unit (BS) and a mixture of formalin-inactivated whole cell ETEC bacteria expressing colonization factors (the BS-CFA ETEC vaccine). The vaccine has been found to be safe and immunogenic in Phase I studies carried out in Sweden, Egypt and Bangladesh. A phase I, safety and immunogenicity study in children in Bangladesh has shown that the vaccine is safe and gives rise to significant antibody responses. A phase II study in children in Egypt has shown that the vaccine is sufficiently safe and immunogenic in children to justify proceeding to evaluation in infants and to phase III, safety and efficacy studies. We hypothesize that the vaccine should be suitable for children in Bangladesh. In order to test the hypothesis, the vaccine needs to be tested in a larger group of children in the field setting, initially in a phase II trial. This information is needed before testing the vaccine in studies on the protective efficacy of the vaccine in the pediatric age group in the field.

| Principal Investigator: Last, first, middle_ |  |
|--|--|
|--|--|

# **Specific Aims:**

Describe the specific aims of the proposed study. State the specific parameters, biological functions/ rates/ processes that will be assessed by specific methods (TYPE WITHIN LIMITS).

- A. Determine the safety of the oral BS-CFA ETEC vaccine in healthy Bangladeshi children aged 6 months to 3 years in a randomized double-blind placebo-controlled trial.
- B. Determine the immunogenicity of the vaccine in a subset of the children by studying.
  - 1. the antibody secreting cell (ASC) responses to the vaccine components (CFs and BS) prior to vaccination and after each of the two vaccine doses.
  - 2. the antibody response in plasma and faeces to the vaccine components prior to vaccination and after each of the two vaccine doses.
  - 3. the cellular response to the vaccine components by analyzing the cytokine responses in plasma, faeces and stimulated peripheral blood mononuclear cells.

# **Background of the Project including Preliminary Observations**

Describe the relevant background of the proposed study. Discuss the previous related works on the subject by citing specific references. Describe logically how the present hypothesis is supported by the relevant background observations including any preliminary results that may be available. Critically analyze available knowledge in the field of the proposed study and discuss the questions and gaps in the knowledge that need to be fulfilled to achieve the proposed goals. Provide scientific validity of the hypothesis on the basis of background information. If there is no sufficient information on the subject, indicate the need to develop new knowledge. Also include the **significance and rationale** of the proposed work by specifically discussing how these accomplishments will bring benefit to human health in relation to biomedical, social, and environmental perspectives. (DO NOT EXCEED 5 PAGES, USE CONTINUATION SHEETS).

#### Burden of disease due to ETEC diarrhoea

It has been estimated that ETEC infections alone cause approximately 210 million episodes of diarrhoea and over 380,000 deaths annually in children under 5 years of age (WHO, 1996, 1999). The peak of incidence of ETEC diarrhoea in endemic countries occurs in the first year of life, with a declining incidence with age thereafter. Of the 7-8 episodes of diarrhoea annually in children, in the developing world, at least 2-4 attacks may be due to ETEC (Black, 1993). As a result, ETEC diarrhoea may contribute to growth retardation and death in these children. In addition, it is responsible for over 50% of diarrhoea in travellers to ETEC endemic regions of the world. A high proportion of diarrhoeal illness in military personnel is also caused by ETEC (Wolf *et al.*, 1997). The clinical symptoms of the disease are watery diarrhoea often accompanied by abdominal cramps, malaise and low grade fever. It may last 3-7 days and the disease spectrum can range from mild diarrhoea to dehydrating cholera-like symptoms, which is seen in about 5% of cases (Black, 1986).

The pathogenicity of ETEC is due to their ability to colonize the small intestine and to produce one or both of two types of toxins, the heat stable enterotoxin (ST) (Field et al., 1978) and/or the heat labile enterotoxin (LT)

| $\mathbf{p}_1$ | rincinal | Investigator: | Lact  | first | middle |
|----------------|----------|---------------|-------|-------|--------|
| 1              | шуграг   | mivesugator.  | Last. | HESL  | magae  |

([name] and Holmgren, 1978). These bacteria also possess a variety of surface located adhesins that anchor them to the intestinal mucosal receptors (Gaastra and de Graaf, 1982; Evans and Evans, 1998). This anchorage enables the bacteria to resist the flushing action of the intestinal peristalsis and the toxins are delivered close to the enterocytes. The adhesins are termed colonization factors (CFs) and may be fimbrial, fibrillar or non-fimbrial in structure. Some 20 adhesins have been identified on human ETEC strains (Gaastra and [name], 1996). Of these structures, CFA/I consists of a single subunit, whereas CFA/II may consist of three antigenically separate CS antigens, CS1, CS2 and CS3 (Smyth, 1982). Likewise, it has been found that CFA/IV may consist of CS4, CS5 and CS6 (Thomas et al., 1985).

Epidemiological studies carried out in various geographical areas show a large variation in the prevalence of CFs in ETEC isolated in the different regions (Gaastra and [name], 1996). However, the 7 best characterized CFs are CFA/I, CS1, CS2, CS3 (CFA/II components), CS4, CS5 and CS6 (CFA/IV components). These have been found in 50-80% of clinical ETEC isolates worldwide (Giron et al., 1995). In some areas CFA/I and CFA/IV are common (Lopez-Vidal et al., 1990; Gothefors et al., 1994), whereas in others CFA/II may be more prevalent (Wolf et al., 1993; Levine et al., 1993). In a study carried out in Bangladesh from 1980 to 1982, it was observed that CFA/I and CFA/II were commonly present on ETEC (Gothefors et al., 1985). However, in a study, that has been conducted recently in Bangladesh on the 2% surveillance patients with diarrhoea at ICDDR,B where screening for 12 different CFs was carried out, CFA/I, CFA/II and CFA/IV were detected in the highest frequencies in ETEC (Qadri et al., manuscript submitted).

#### **Protection from ETEC disease**

For ETEC, which are noninvasive, antibodies that can be induced locally in the gut are believed to be protective (Levine, 1990). Both antibacterial (mainly directed against CFs) and antitoxic antibodies act synergistically to provide protection (Ahren and [name], 1982). Protective immunity is dependent on the stimulation of the mucosal immune system and generation of secretory IgA antibodies in the gut-associated lymphoid tissue. Studies in animal models and human volunteers suggest that primary ETEC infections can protect against re-infections (Levine et al., 1984; [name] et al., 1990). Natural ETEC infection also appears to be protective. This is evident since the highest incidence of the disease is in the age group of 6-36 months and the rate of illness decreases with age, suggesting the development of protective immunity (Black et al., 1986). In a prospective study recently conducted in ICDDR,B, the highest incidence of ETEC was in children less that 5 years of age. About 74% of ETEC were isolated from diarrhoeal children less than 5 years of age, of whom 93% were up to 3 years of age (Qadri et al., manuscript submitted). It was observed that the incidence of ETEC diarrhoea increased from 3 months of age.

ETEC diarrhoea also gives rise to specific antibody secreting cell (ASC) responses which can be detected in the peripheral blood as well as in the small intestinal biopsies. An increase in CF and toxin-specific ASC responses were seen very early after onset of illness. The peripheral blood B cell responses are believed to be derived from the GALT, which after circulating in the blood, home-back to the mucosa for antibody secretion (Czerkinsky et al., 1987). Therefore, these cells appear to be good markers of the immune response of the GALT to locally presented antigens. Determination of the specific B cell responses in peripheral blood has been found to be a reliable proxy measure of the mucosal immune response in the gut. Antibody production and B cell function are dependent on T cells which control the proliferation and differentiation of B cells and is, therefore, dependent on signaling by cytokines.

T cell responses have been studied to the BS-CFA ETEC vaccine in adults (Wenneras et al., 1994). Immunization of Swedish volunteers resulted in increases of IFN-gamma but not IL-2. Of the studies carried

| Principal Investigator: Last, firs | st, middle |  |
|------------------------------------|------------|--|
| • •                                | •          |  |

out on adult vaccinees and patients in endemic regions, preliminary results indicate that a wide array of cytokines may be induced although there seems to be less of IFN-gamma being detected *in vitro* (Qadri *et al.*, manuscript in preparation). However, the response seen in adults is that of a secondary nature and studies have not been carried out in children who have been vaccinated. Such a study needs to be carried out in order to better understand which cytokines are involved in the induction of the antibody responses.

ETEC infection is spread through water or food contaminated by faeces from infected persons. The disease can effectively be prevented if clean water and food and good sanitary conditions are made available in the developing countries. However, since this is not be possible to accomplish in the near future, the other alternative for the prevention of the disease would be the availability of a vaccine that is cheap and effective. The vaccine should be easily administered to infants and children, who are the most vulnerable to infections.

# Research Design and Methods

Describe in detail the methods and procedures that will be used to accomplish the objectives and specific aims of the project. Discuss the alternative methods that are available and justify the use of the method proposed in the study. Justify the scientific validity of the methodological approach (biomedical, social, or environmental) as an investigation tool to achieve the specific aims. Discuss the limitations and difficulties of the proposed procedures and sufficiently justify the use of them. Discuss the ethical issues related to biomedical and social research for employing special procedures, such as invasive procedures in sick children, use of isotopes or any other hazardous materials, or social questionnaires relating to individual privacy. Point out safety procedures to be observed for protection of individuals during any situations or materials that may be injurious to human health. The methodology section should be sufficiently descriptive to allow the reviewers to make valid and unambiguous assessment of the project. (DO NOT EXCEED TEN PAGES, USE CONTINUATION SHEETS).

| Principal Investigator: Last, first, middl |  |
|--|--|
|  |  |

#### d) Research Plan, Research design and Methods Study Design

This vaccine study will be a randomized, double blinded, placebo controlled trial. Children will be stratified by age (in two age bands, 6 months to 18 months, > 18 months to 3 years) before randomization. In each group each subject will be assigned a sequential number at the time of initial dosing, corresponding to sequentially numbered and randomized set of two single-dose vials of study agent. The codes will be broken after all clinical and laboratory evaluation have been completed.

#### Selection of study subjects

Before entering into the study children in the different age groups will be screened from the slums and history recorded (Appendix III). Although 158 children need to be recruited in the two age groups, more will be screened to obtain study subjects which meet the inclusion criteria. Previous experience in similar studies (Protocol No.98-001) has shown that around 30 to 40% more have to be screened. The children will be carefully examined by a physician. A detailed history of the volunteer of previous immunizations, nutritional status, recent illness (as outlined below) that can compromise the immune system, family background etc. will be taken (Appendix III). Healthy male and female children will be recruited from the urban slums.

Children will be excluded from enrollment if interviewers find: (a) a history of chronic gastrointestinal disorder, (b) diarrhoeal illness in the past 2 weeks (diarrhoea being defined as passing of  $\geq$  3 loose or liquid stools in 24 hours (c) febrile illness in the preceding week, or (d) other serious chronic illness (e) had antibiotic treatment at least 7 days prior to the enrollment in the study (f) children suffering from second or third degree of protein energy malnutrition (PEM).

A routine stool microscopic examination and culture for common enteric pathogens including ETEC will be carried out three days prior to vaccination. Children whose stools are postive for ETEC will not be vaccinated since this will interfere in the evaluation of the response to the vaccine When immunization for the second dose of the vaccine will be carried out (14 days after the first dose) children who have fever or diarrhoea will be excluded from the study.

The nutritional level of the children will be monitored using anthropometric measurements (weight-for-age, and weight-for-length/height). Children below > -2SD of the NCHS will not be enrolled. We plan to recruit children in the 6 month -3 year range for immunization.

#### Sample size calculation

Sample size calculation (N) has been carried out using the formula shown below at a power of 80% and significant difference level at 95%. The number to be recruited for the safety studies on the vaccine has been derived using side-effects data obtained in a similar study (Savarino *et al.*, 1999). Here  $p_1 = 1\%$  and  $p_2 = 11\%$ , (ETEC vaccinees =  $p_1$ ,; placebo control =  $p_2$ ,  $d = p_1 - p_2$ ). Therefore:

$$N = \frac{(Z\alpha/2 + Z\beta)^2 (2pq)}{d^2}$$

A sample size of 106 is calculated for each of the age groups (6 months to 18 years, >18 month to 3 years) in the study population. Considering a 20% prevalence of ETEC and taking into consideration a 15% adjustment of dropout, the number is 126. However since the prevalence of diarrhoea in the population in the

Principal Investigator: Last, first, middle children in this age group is about 25% (Baqui et al. 1993), and this is taken into consideration, 158 children will be recruited in each age group. The subset of study subjects to be studied for the immune response studies from the groups above have similarly been obtained by using conservative estimations (data for the response obtained to the CF antigen CS4, to which the frequency of response was the lowest). Here  $p_1 = 40\%$  and  $p_2 = 11\%$ , a sample size of 40 and with adjustment for 15% dropout, the number to be recruited is 46 in each age group for both the study groups.

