#### Data analysis

Baseline characteristics of the vaccine and placebo groups will be examined for group comparability. Any baseline difference will be controlled for during data analysis. The data for the two age groups will be handled together and will also be analyzed separately to evaluate the responses.

The frequency distribution will be examined to assess the distribution of data. If the data is not normally distributed, decisions about data transformation and on appropriateness of statistical tests will be made. The data from the vaccine and placebo group will be compared to compare the safety of the vaccine by assessing the association with adverse events in each group.

The data from the two groups will also be compared for assessing the immunogenicity of the vaccine. This will be done for the ASC, plasma antibody and faecal antibodies using criteria described above for defining a response in the study subjects.

All subjects receiving at least one dose of study agent will be included in the postdosing safety analysis. The profile likelihood method will be used to assess differences in the proportions of primary outcomes in vaccinees versus placebo recipients after each dose (Newcombe, 1998). For individual symptoms, proportions will be compared with Fisher's Exact test. This test will also be used to assess differences in the occurrence of ASC responses and antibody seroconversion between the two groups after each dose. The number of antigen specific ASC after each dose will be compared between treatment groups by the median test. Within the vaccine group, the one sample rank sum Wilcoxon test will be used to assess whether number of ASC and plasma antibody titer fold increases are boosted after each successive dose. All statistical tests will be interpreted in a two-tailed fashion.

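### The safety sample size is a per-arm number assigned to whole age groups, and its inflation steps and totals do not agree; 80% power per age group is not established as written

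*Protocol*

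**What the plan says.** The Sample size calculation section sizes the safety comparison "at a power of 80% and significant difference level at 95" percent. It takes event proportions of 1% in vaccinees and 11% in placebo recipients from an earlier study, and prints a two-proportion formula with a 2pq term over the squared difference. It then gives three figures:

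- The starting size: "A sample size of 106 is calculated for each of the age groups".
- After a 20% ETEC prevalence and a dropout allowance: "taking into consideration a 15% adjustment of dropout, the number is 126".
- After a further allowance for a 25% prevalence of diarrhoea: "158 children will be recruited in each age group".

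Selection of study subjects restates the target differently: "Although 158 children need to be recruited in the two age groups".

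Under Study Design, age is a stratum and children are randomised to vaccine or placebo within it. No allocation ratio is given, and none of 106, 126 or 158 is described as per arm or as a total over arms. Data analysis says the age groups will be handled together and also separately, and that "All statistical tests will be interpreted in a two-tailed fashion". It assigns the primary safety outcome, after each dose, to the profile likelihood method. Fisher's exact test is for individual symptoms and for immune responses.

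**The concern.** A formula of this form returns the size of one of two equal groups. The text attaches its result to an age group that contains both groups and never doubles it. Taken literally, each age group gets about half the children that the calculation calls for, before an inflation that does not multiply out. Safety is the first specific aim, and the youngest stratum, 6 to 18 months, is the one nearest to the extension to children from 3 months that the protocol foresees. If the 80% does not hold within that stratum, a comparison there showing no difference says less than the protocol implies. Separately, the text supports more than one total, so recruitment staff and readers cannot tell how large the trial is meant to be.

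**Working it through.** **Inputs.** Two-sided 5% (Data analysis) and 80% power: z = 1.960 and 0.8416, (1.960 + 0.8416)² = 7.849. Proportions 0.01 and 0.11, d = 0.10. The protocol does not define p and q; I take p as the mean, 0.06, and q = 0.94. Allocation 1:1 is my assumption.

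**1. The printed formula.** N = 7.849 × 2 × 0.06 × 0.94 / 0.10² = 88.5, so 89 **per arm**. The 2 in 2pq comes from the variance of a difference between two equal groups. This does not give 106.

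**2. Where 106 comes from.** The version with separate null and alternative variances gives n = 87.3 per arm. The usual continuity correction, (n/4) × [1 + √(1 + 4/(n d))]², turns 87.3 into 106.4, which matches. The same method for the immune-response subset (40% versus 11%) gives 40.9, against the stated 40. Both are per-arm sizes. The other variants tried (unpooled variance 85, one-sided 69 to 70, 90% power 117 to 119) miss 106 and are per arm as well.

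**3. What an age group then needs.** 2 × 89 = 178 evaluable children by the printed formula, or 2 × 106 = 212 with the correction. The literal 158 is below both before any loss.

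**4. The inflation chain.**

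| Step | Arithmetic | Result |
|---|---|---|
| 15% alone | 106 × 1.15, or 106 / 0.85 | 122, or 125 |
| 20% alone | 106 × 1.20, or 106 / 0.80 | 127, or 132.5 |
| Both | 106 × 1.20 × 1.15, or 106 / 0.80 / 0.85 | 146, or 156 |
| Stated | | 126 |
| Then 25% | 126 × 1.25 | 157.5, stated 158 |
| All three | 146.3 × 1.25, or 155.9 / 0.75 | 183, or 208 |

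Only the last stated step reproduces. The figure 126 is close to applying one adjustment, not two.

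**5. Power on the literal reading.** With 158 per age group, 79 are in each arm. A 15% loss leaves 158 × 0.85 / 2 = 67 per arm. The uninflated 106 is 53 per arm. The normal approximation matches the sample-size method. The last column is exact enumeration of the likelihood-ratio test of no difference, which corresponds to a profile-likelihood interval excluding zero.

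| Per arm, one age group | Normal approximation | Likelihood ratio, nominal |
|---|---|---|
| 79 | 76% | 87% |
| 67 | 69% | 82% |
| 53 | 58% | 74% |

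The likelihood-ratio figures are flattering: at these sizes the test's true type I error reaches about 9% for some common event proportions.

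**6. Pooled age groups.** 158 per arm gives 97%, and 134 per arm (158 × 0.85) gives 94%, by the normal approximation.

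**7. If 158 is per arm.** Each age group has 316 children, the trial has 632, and power per age group is about 97%. Neither 316 nor 632 is stated as a target.

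**The case against.** A reader might infer that the protocol demonstrably halves its requirement, so that every age-group comparison is underpowered. The text does not support that as a certainty. It never calls 106 or 158 a total over both arms. The immune-response subset is given as 46 in each age group for both study groups, which can be read as 46 per arm. The clarification list says samples come from about a third of the children, and 46/158 = 29%, which suggests that 46 and 158 are on the same basis. If one is per arm, so is the other. That does not settle the question, because the ratio is the same if both are per age group, but it keeps the per-arm reading open.

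The choice of test also matters. Fisher's exact test would give lower power (69% at 79 per arm), but it is not the planned test for the primary outcome. On the planned profile likelihood method, 79 per arm nominally exceeds 80%. That stands as a caution against one firm power figure. It does not rescue the stated calculation, which rests on a normal approximation, and the nominal gain comes partly from an inflated type I error.

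Two further points stand in part. Every child with at least one dose stays in the safety analysis, so 79 per arm is the natural row after the first dose, and the smaller rows are sensitivity figures. The sentence about 158 in the two age groups may be loose wording for 158 in each, so I do not rest a power figure on the smaller total. No passage makes a non-significant test the criterion for safety.

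**Conclusion.** The sample-size paragraph is wrong as written, and three faults hold on any reading. The printed formula gives 89, not 106. The step from 106 to 126 does not apply both adjustments named for it. The two sections state the recruitment target differently.

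The effect on power is conditional. On the literal reading, with 1:1 allocation and the stated 1% and 11%, power per age group by the sample-size method's own approximation is 76% with no losses and 58 to 69% at the smaller sizes, not 80%. The pooled comparison is adequate at about 94 to 97%. On the per-arm reading, power per age group is about 97% and the fault is confined to wording and arithmetic. The protocol does not say which was intended.

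**What to change.** In Sample size calculation:

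- State the allocation ratio and the number of children per arm, per age group and in total.
- Name the formula actually used: 89 per arm as printed, or 106 per arm with the continuity correction.
- Replace the 106, 126, 158 sequence with one in which each named adjustment is applied and multiplies out.

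Make Selection of study subjects give the same target.

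If 158 per age group is the intended size, attach the 80% claim to the age-stratified pooled comparison, and restate the lower power of each age-group comparison for the planned primary method, noting that method's type I error at these sizes. If 158 per arm was intended, say so and show the totals of 316 and 632.

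The cost is protocol wording. On the first reading no children are added, but the stated power per age group becomes less favourable. On the second, the larger total has to be stated and the recruitment plan checked against it.

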**Blood**: Venous blood will be collected from the vaccinees prior to immunization and 7 days after intake of each dose of the vaccine. About 3 ml blood will be collected from vaccinees in the age group ranging from 2-3 years of age, in younger children (<18 months) 1.5 ml of blood samples will be collected. For the children in the 6 months to 18 months of age since the volume of blood will be less, these will only be used only for antibody assays. Total and differential counts of blood and hematocrit will be carried out in the clinical laboratory of ICDDR,B. Cytokine responses will be studied in the serum and in the feces. In older children, ASC responses and cytokine assays with stimulation with CF antigens will be carried out.

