#### Detection of antibody secreting cells (ASCs)

The Ficoll-separated MNCs will be assayed for total and ETEC -specific numbers of ASC by the two-colour ELISPOT technique (Czerkinsky et al., 1988; Wenneras et al., 1992). Purified vaccine-specific CF-ASC response of the IgA/IgM isotype (CFA/I and, CS1) (Evans et al., 1979, Klemm et al., 1985) and recombinant CTB-ASC response of the IgA/IgM isotype (Sanchez et al., 1989) will be used. A significant response will be determined if the vaccine specific ASC response as  $\geq 2$  fold increase over baseline value of ASC/ $10^7$  MNC in the baseline sample. Only ASC levels  $\geq 10$  ASCs per  $10^7$  MNCs in the post immunization specimen will be considered a responder.

| Principal ! | westigator: Last | , first, | middle |  |  | <del>-</del> |  |  |
|-------------|------------------|----------|--------|--|--|--------------|--|--|
|-------------|------------------|----------|--------|--|--|--------------|--|--|

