#### Clarification of points as required in the attached list are as follows:

- 1. Only children in the 6 month to 3 year age range will be included since ETEC diarrhoea is a major cause of morbidity and mortality in this age and a vaccine is needed urgently for them. Only children whose guardians or parents have given voluntary consent to participate in this study will be enrolled.
- 2. Methods used have very little chance of physical risk.
- 3. Since only blood will be collected there is little risk other than a minimum discomfort at puncture site. After feeding the oral ETEC vaccine the child will be kept under observation for 30 minutes and will also be monitored for side-effects for 3 consecutive days.
- 4. The interview records will be kept in a locker under supervision. Only the investigators will have access to it.
- 5. Informed consent will be obtained from the guardian or parent of the child. The potential risks and the procedures to be carried out are mentioned in the consent form.
- 6. The interview will be conducted in the homes of the children for obtaining history prior to enrollment. Monitoring the side-effects will also be carried out in subsequent home visits. Approximately 30 minutes to 1 hour will be required for the interview.
- 7. The vaccine trial will benefit children in any ETEC endemic country if the trial shows that the vaccine is safe and immunogenic. This will lead to future studies for effectiveness.

| Principal Investigator: Last, first, middle  8. The activity will require collection of stool an children that will be enrolled in the study.   | d small amount of blood from about a third of the total  |
|---|--|

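### The immunogenicity subset of 46 per age group appears to spread a per-arm sample size over both arms, so power within one age group is about 45–62% at the planning rates, not 80%; pooling repairs this for antibody but not for ASC

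*Protocol*

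**What the plan says.** The section Sample size calculation works "at a power of 80% and significant difference level at 95" per cent, with a two-group formula N = (Zα/2 + Zβ)² × 2pq / d². For the immunogenicity subset it takes p1 = 40% and p2 = 11%, described as conservative because they rest on "data for the response obtained to the CF antigen CS4, to which the frequency of response was the lowest". It states a sample size of 40 and a 15% dropout adjustment, and concludes that "the number to be recruited is 46 in each age group for both the study groups". The same section recruits 158 children in each age group for safety.

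Three other places bear on this:

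- The clarification list, item 8, says that the study needs stool and a "small amount of blood from about a third of the total" number of enrolled children.
- Under Safety Monitoring of the Vaccine, the paragraph on blood restricts samples from the 6–18 month group to antibody assays and adds: "In older children, ASC responses and cytokine assays with stimulation with CF antigens will be carried out".
- Data analysis examines the age groups together and separately, and names Fisher's exact test for comparing ASC responses and seroconversion between arms. It adds: "All statistical tests will be interpreted in a two-tailed fashion".

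ASC responses are tested against CFA/I, CS1 and CTB. The plasma ELISA is against CFA/I and CTB. The antigens for the faecal assay are not listed.

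**The concern.** A two-group formula returns the number needed in each arm. The text then appears to use that number as the total for both arms within an age group, which would halve the size behind the 80% claim. Pooling the age groups would double it again for antibody endpoints. ASC response, listed first under Specific Aim B, exists only in the older group and gains nothing from pooling. If so, the stated 80% is wrong for every single-age-group comparison of responder rates, and a true difference of 40% against 11% would be missed about half the time there.

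**Working it through.** **Inputs.** p1 = 0.40, p2 = 0.11, power 80% and a 95% level from Sample size calculation; two-sided testing from Data analysis. No allocation ratio is stated; I assume 1:1, which the equal-arm formula implies. So d = 0.29, p = 0.255, q = 0.745.

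**1. Reproducing the 40.**
- Printed formula: (1.96 + 0.8416)² × 2 × 0.255 × 0.745 / 0.29² = 35.5 per arm.
- Version with separate variances under the alternative: 34.3 per arm. With continuity correction, (34.3/4) × [1 + √(1 + 4/(34.3 × 0.29))]² = 40.9 per arm.
- Both arms together by the printed formula: 2 × 35.5 = 71.

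The stated 40 therefore matches a continuity-corrected number per arm and cannot be a two-arm total. The dropout step is 40 × 1.15 = 46. The safety figure behaves the same way: the continuity-corrected result for 1% against 11% is 107 per arm, against 106 stated.

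**2. Which unit does the 46 carry?** The share of children giving blood is a check.

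| Reading of 46 | Reading of 158 | Share giving blood |
|---|---|---|
| both arms, per age group | per age group | 92/316 = 29% |
| each arm, per age group | per age group | 184/316 = 58% |
| each arm, per age group | each arm, per age group | 184/632 = 29% |

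With 158 per age group, as written, about a third fits only the first row. The third row also fits, but needs a reading of 158 that the sample size section does not give.

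**3. Power at 40% against 11%.** In the first row each arm has 46/2 = 23 children. Removing the dropout allowance leaves 46/1.15 = 40 evaluable, or 20 per arm. The normal approximation is Φ{[d√n − 1.96√(2pq)] / √(p1q1 + p2q2)}:
- n = 23: (1.391 − 1.208)/0.581 = 0.314, power 62%.
- n = 20: (1.297 − 1.208)/0.581 = 0.153, power 56%.

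Power of the two-sided Fisher test is by full enumeration of outcomes.

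| Comparison | Per arm | Fisher | Normal |
|---|---|---|---|
| One age group, as recruited | 23 | 53% | 62% |
| One age group, after dropout | 20 | 45% | 56% |
| Both age groups pooled, after dropout | 40 | 82% | 86% |
| Both age groups pooled, as recruited | 46 | 87% | 90% |

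**4. ASC.** The assay is confined to older children, so the first two rows are the relevant ones. Against 11% in the placebo arm, 80% Fisher power needs a vaccine response of about 51% with 23 per arm and about 55% with 20 per arm, rather than 40%.

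**The case against.** The strongest reply is that the sentence can mean 46 for each study group. That follows directly from a per-arm formula, and power is then met (82% by Fisher with 40 evaluable per arm). The blood-sampling share does not exclude it, because 46/158 is 29% whenever both numbers carry the same unit. Selection of study subjects blurs the denominator further by mentioning 158 children in the two age groups. This reading stands as a possibility. It requires 158 also to be per arm, however, against the statement that 158 are recruited in each age group. If only the 46 is per arm, the sampled share is 58% and item 8 of the clarification list is wrong. On either reading some text must change.

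The second reply is that CS4 was chosen as the weakest responder, so ASC power for CFA/I, CS1 or CTB could be higher. That stands too. Planning on the lowest responder is not in itself an error, and at a 60% response Fisher power would be 89–93% with 20–23 per arm. But the documents give no rates for the assayed antigens, so neither 80% nor any other figure is documented for them.

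Third, responder proportions are not the only ASC analysis. Data analysis also plans a median test between arms and within-vaccine-group rank tests. The stated 80%, however, belongs to the comparison of proportions.

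A reader might go further and infer that ASC is tested with half the claimed sensitivity, or that a negative ASC result could stop a working vaccine. The documents support neither: 45–62% is more than half of 80%, no go/no-go rule is tied to ASC, and the only designated primary endpoint is safety.

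**Conclusion.** The stated 80% does not hold for a single age group on the most natural reading of the text. At the protocol's own rates, power there is 53–62% with 23 per arm and 45–56% after the planned dropout. It reaches at least 80% only for antibody endpoints pooled over the age groups (82–87% by Fisher), an analysis already planned. The ASC responder comparison cannot use that route.

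This rests on three assumptions: 46 covers both arms, which is likely but not certain; allocation is 1:1; and the 40% and 11% rates apply. The last matters most for ASC, because those rates are for CS4, which is not among the antigens named for that assay. The 45–62% is therefore power at the planning rates, not an estimate of the true power for ASC.

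**What to change.** In Sample size calculation:

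1. State the subset size per arm and per age group, with the allocation ratio, and reconcile it with the 158 and with the share of children giving blood in item 8 of the clarification list.
2. If 46 covers both arms, restate power by endpoint: about 45–62% for responder comparisons within one age group, including ASC, at 40% against 11%; at least 80% only for plasma and faecal antibody pooled over age groups.
3. Note that the planning rates are for CS4, which is not named for the ASC or plasma assays, and that 80% Fisher power for ASC would need a vaccine response of about 51–55% against 11%.
4. If 46 per arm in each age group was intended, say so and correct the statement about a third of the children.

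Items 1 to 3 cost only wording and a less favourable stated power; they require no extra children or blood samples. Item 4 would mean acknowledging 184 sampled children rather than 92, which the ethics documents should then reflect.
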